## **4.2. Scientific Rationale for Study Design**

### **Blinding, Control, Study Phase/Periods, Intervention Groups**

A placebo control will be used to establish the frequency and magnitude of changes in clinical endpoints that may occur in the absence of active intervention. Adalimumab (HUMIRA) is approved for the treatment of moderate to severe HS and was selected as a reference arm to benchmark bermekimab efficacy relative to adalimumab. Randomization will be used to minimize bias in the assignment of participants to intervention groups, to increase the likelihood that known and unknown participant attributes (e.g., demographic and baseline characteristics) are evenly balanced across intervention groups, and to enhance the validity of statistical comparisons across intervention groups. Blinded intervention will be used to reduce potential bias during data collection and evaluation of clinical endpoints.

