#### **5.1. Inclusion Criteria**

Each potential participant must satisfy all of the following criteria to be enrolled in the study:

1. Be a male or female 18 (or the legal consent in the jurisdiction in which the study is taking place) years of age or older.
2. Be otherwise healthy on the basis of physical examination, medical history, vital signs, and 12-lead ECG performed at screening. Any abnormalities, must be consistent with the

underlying illness in the study population and this determination must be recorded in the participant's source documents and initialed by the investigator.

3. Have HS for at least 1 year (365 days) prior to the baseline visit as determined by the investigator through participant interview and/or review of the medical history.
4. Have HS lesions present in at least 2 distinct anatomic areas (examples include but are not limited to left and right axilla; or left axilla and left inguocrural fold) at screening and baseline visits.
5. Have Hurley Stage II or Hurley Stage III HS as determined by the investigator at screening and baseline visits.
6. Had an inadequate response to a course of appropriate oral antibiotics for treatment of HS (or demonstrated intolerance to or had a contraindication to oral antibiotics for treatment of their HS) in the investigator's opinion.
7. Criterion modified per Amendment 2.

7.1. Be considered, in the opinion of the investigator, a suitable candidate for adalimumab (HUMIRA®) therapy according to their country's approved HUMIRA product labeling. This criterion only applies to participants enrolling in Part 1 of the study, where adalimumab is one of the possible randomization arms. This criterion does not apply to participants enrolling in Part 2.

8. Have stable HS for at least 60 days prior to the screening visit and at baseline as determined by the investigator through patient interview and/or review of the medical history.
9. Have a total AN count of  $\geq 5$  at the screening and baseline visit.
10. Have screening laboratory test results within the following parameters, if one or more of the laboratory parameters is out of range, a single retest of laboratory values is permitted:
  - a. Hemoglobin  $\geq 10$  g/dL (SI:  $\geq 100$  g/L)
  - b. White blood cells  $\geq 3.5 \times 10^3/\mu\text{L}$  (SI:  $\geq 3.5$  GI/L)
  - c. Neutrophils  $\geq 1.5 \times 10^3/\mu\text{L}$  (SI:  $\geq 1.5$  GI/L)
  - d. Platelets  $\geq 100 \times 10^3/\mu\text{L}$  (SI:  $\geq 100$  GI/L)

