**AND**

- (ii) with absence of ALL conditions (a), (b), (c) above during the period between the negative test result and the baseline study visit.

NOTES on COVID-related exclusion:

- The field of COVID-related testing (for presence of, and immunity to, the SARS-CoV-2 virus) is rapidly evolving. Additional testing may be performed as part of screening and/or during the study if deemed necessary by the investigator and in accordance with current regulations / guidance from authorities / standards of care.
- Precaution: for those who may carry a higher risk for severe COVID-19 illness, follow guidance from local health authorities when weighing the potential benefits and risks of enrolling in the study, and during participation in the study.

12. Criterion modified per Amendment 2.

12.1. Has a history of latent or active granulomatous infection, including histoplasmosis or coccidioidomycosis, before screening. Participants with radiographic evidence of possible prior histoplasmosis or coccidioidomycosis will be

excluded. Refer to Inclusion Criterion 13 for information regarding eligibility with a history of latent TB.

13. Has a chest radiograph or a chest CT scan within 3 months before the first administration of study intervention that shows an abnormality suggestive of a malignancy or current active infection, including TB.
14. Has ever had a nontuberculous mycobacterial infection or opportunistic infection (eg, cytomegalovirus, pneumocystis, aspergillosis).
15. Has 2 indeterminate (on repeat sampling) QuantiFERON -TB test results.
16. Has had major surgery (e.g., requiring general anesthesia and hospitalization) within 8 weeks before screening, or has not fully recovered from such surgery, or has such surgery planned during the time the participant is expected to participate in the study.

**NOTE:** Participants with planned surgical procedures to be conducted under local anesthesia may participate.

17. Has a transplanted organ (with exception of a corneal transplant >3 months before the first administration of study intervention).
18. Has known allergies, hypersensitivity, or intolerance to bermekimab or adalimumab or its excipients (refer to IB).
19. Criterion modified per Amendment 2.

19.1. Has previously received adalimumab. This criterion only applies to participants enrolling in Part 1 of the study, where adalimumab is one of the possible randomization arms. This criterion does not apply to participants enrolling in Part 2.

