If favorable efficacy is observed in either the first or the second interim analysis, screening and randomization of participants will resume in Part 2 as planned, with additional participants being randomized to receive bermekimab 1050 mg qw, placebo, bermekimab 1050 mg qw→q2w, or bermekimab 700 mg qw→q2w in a 1:1:2:2 ratio (approximately 25 participants randomized to receive bermekimab 1050 mg qw and placebo, respectively, and approximately 50 participants randomized to receive bermekimab 1050 mg qw→q2w and bermekimab 700 mg qw→q2w, respectively).

However, if 700 mg qw→q2w is not included in Part 2 based on PK results from Part 1, screening and randomization of participants will resume with additional participants being randomized to receive bermekimab 1050 mg qw, placebo, or bermekimab 1050 mg qw→q2w in a 1:1:2 ratio (approximately 25 participants randomized to receive bermekimab 1050 mg qw and placebo, respectively, and approximately 50 participants randomized to receive bermekimab 1050 mg qw→q2w). Thus, if the study continues, a total number of approximately 250 or 300 participants will be enrolled in the study.

Otherwise, enrollment will remain paused while the sponsor considers whether to terminate the study at that point for insufficient efficacy, to resume enrollment as planned, or to resume the study with modification.

The requestor must use his or her own user identification and personal identification number when contacting the IWRS and will then give the relevant participant details to uniquely identify the participant.

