- From comparison between adalimumab with placebo using data from part 1 only for the primary endpoint, the study sample size provides 83% power to detect a 25% (50% vs 25%) treatment difference with 50 participants per arm.

No formal comparisons will be performed between the bermekimab 1050 mg qw group and the adalimumab group from Part 1, however the treatment difference and its 2-sided 80% CI for the primary endpoint at Week 16 between these 2 groups will be provided. A sample size of 50 participants in each of the treatment groups will produce a 2-sided 80% CI for the treatment difference with a width of approximately 29%.

Comparisons between treatment groups at Week 12 with combining Part 1 and Part 2 data

Assuming HiSCR50 response rates at Week 12 are 25% to 35% for placebo and 50% to 75% for the bermekimab groups, respectively; based on these assumptions, approximately 250 participants across Part 1 and Part 2 are planned to be randomized to the placebo (n=75), bermekimab 700 mg qw to q2w (n=50), bermekimab 1050 mg qw to q2w (n=50), and bermekimab 1050 mg qw (n=75) treatment groups. Comparisons between the bermekimab groups and the placebo groups will be based on data combining Part 1 and Part 2.

For comparisons between bermekimab groups with placebo combining Part 1 and Part 2 for the primary endpoint, bermekimab 1050 mg qw and 1050 mg qw → q2w groups will be grouped together as bermekimab 1050 mg group (n=125) and 700 mg qw → q2w group will be denoted as bermekimab 700 mg group, the study sample size provides:

- At least 87% power to detect a 25% treatment difference between the bermekimab 700 mg treatment group (n=50) and the placebo group (n=75).
- 97% power to detect a 25% (50% vs 25%) treatment difference between the bermekimab 1050 mg treatment group (n=125) and the placebo group (n=75).
- Greater than 99% power to detect a 40% (75% vs 35%) difference between the bermekimab 1050 mg treatment group (n=125) and the placebo group (n=75) or between 700 mg treatment group (n=50) and the placebo group (n=75).

in HiSCR50 at Week 12 combining Part 1 and Part 2 based on a 2-sample Z-test at a Type I error rate of 0.10 (2-sided; [Table 3](#)).

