**Table 3: Power to detect a treatment difference in HiSCR50 at Week 12 Combining Part 1 and Part 2**

Placebo	Treatment Group	Difference	Power
Bermekimab 1050 mg (n=125) vs placebo (n=75)			
25%	50%	25%	97%
25%	55%	30%	>99%
25%	60%	35%	>99%
25%	65%	40%	>99%
25%	70%	45%	>99%
25%	75%	50%	>99%
30%	55%	25%	97%
30%	60%	30%	99%
30%	65%	35%	>99%
30%	70%	40%	>99%
30%	75%	45%	>99%
35%	60%	25%	96%
35%	65%	30%	99%
35%	70%	35%	>99%
35%	75%	40%	>99%
Bermekimab 700 mg (n=50) vs placebo (n=75)			
25%	50%	25%	89%
25%	55%	30%	96%
25%	60%	35%	99%
25%	65%	40%	>99%
25%	70%	45%	>99%
25%	75%	50%	>99%
30%	55%	25%	87%
30%	60%	30%	95%
30%	65%	35%	99%
30%	70%	40%	>99%
30%	75%	45%	>99%
35%	60%	25%	87%
35%	65%	30%	95%
35%	70%	35%	99%
35%	75%	40%	>99%

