#### 9.4.2.1.3. Primary Endpoint Analysis

In the primary efficacy analysis, data from all randomized participants who received at least 1 administration of study intervention will be analyzed according to their assigned treatment group.

In this primary analysis, the proportion of participants who achieve a HiSCR50 at Week 16 in Part 1, and at Week 12 based on the combined data from Part 1 and Part 2 will be summarized for each treatment group. To address the primary objective, a CMH chi-squared statistic stratified by baseline Hurley stage status (II, III) at an alpha level of 0.1 will be used for each of the comparisons between bermekimab treatment groups and placebo group.

There will be 3 comparisons for the primary analyses. The proportion of participants who achieve HiSCR50 will be compared between bermekimab treatment groups and the placebo group based on the fixed-sequence testing approach. To maintain an overall Type I error rate of 0.1, the 3-pairwise comparisons will be performed sequentially at a two-sided alpha level of 0.1 in the following order:

1. Bermekimab 1050 mg group versus Placebo at Week 12 based on the combined data from Part 1 and Part 2
2. Bermekimab 1050 mg group versus Placebo at Week 16 based on the data from Part 1
3. Bermekimab 700 mg group versus Placebo at Week 12 based on the combined data from Part 1 and Part 2

With the pre-specified sequential analyses, whenever a prior comparison is not significant at a two-sided alpha level of 0.1, the remaining treatment group comparisons will be considered nonsignificant and the p-values from the remaining treatment group comparison will be considered nominal.

In addition, the comparison between adalimumab and placebo for the primary endpoint at Week 16 in Part 1 will also be performed.

This method is to control the type-1 error at 10% level or less and will only be implemented for the primary efficacy analysis. The study will be considered positive if one of the hypotheses is tested as significant at a 2-sided alpha level of 0.10.

To examine the robustness of the primary endpoint analysis, additional analyses will be conducted using different missing data approaches; these analyses will be described in the SAP. In addition, sensitivity analyses will be performed for the primary endpoint using the per-protocol population, which includes participants who are generally compliant with the protocol.

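### Two thirds of the placebo group in the 700 mg test comes from Part 1, so its stated power and 10% error rate hold only if placebo response is the same in both Parts

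*Protocol*

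**What the plan says.** Protocol 6.3 randomises about 150 participants 1:1:1 in Part 1 to bermekimab 1050 mg, adalimumab or placebo, then pauses enrolment. Part 2 opens only after a favourable interim result. It randomises "approximately 25 participants randomized to receive bermekimab 1050 mg qw and placebo, respectively", with about 50 on 1050 mg qw→q2w and, if that arm is kept, about 50 on 700 mg qw→q2w.

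Protocol 9.4.2.1.3 sets three comparisons in fixed sequence, each at two-sided 0.10. The third is "Bermekimab 700 mg group versus Placebo at Week 12 based on the combined data from Part 1 and Part 2". Each is a CMH test stratified by Hurley stage. Protocol 9.2 claims "At least 87% power to detect a 25% treatment difference between the bermekimab 700 mg treatment group (n=50) and the placebo group (n=75"), and Table 3 has a block headed "Bermekimab 700 mg (n=50) vs placebo (n=75"). Both are "based on a 2-sample Z-test at a Type I error rate of 0.10 (2-sided"). SAP section 3 repeats the statement and the table.

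Eligibility differs between the Parts. Exclusion 19.1 reads "Has previously received adalimumab. This criterion only applies to participants enrolling in Part 1 of the study". Inclusion 7.1, suitability for adalimumab, ends "This criterion does not apply to participants enrolling in Part 2". For Part 2, exclusion 45 asks only for a 3-month anti-TNF washout. The Amendment 2 summary gives the aim as admitting adalimumab-experienced participants to Part 2.

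Protocol 9.1 words the Week 12 hypothesis as belonging to Part 2, while Primary Estimand 2 (9.4.2.1.2) uses combined data.

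**The concern.** Protocol 4.2 relies on randomisation "to enhance the validity of statistical comparisons across intervention groups". For the 700 mg test, randomisation covers only the Part 2 placebo participants. The Part 1 placebo participants could not have been assigned 700 mg, were enrolled before the pause and were selected under different rules on adalimumab. Any difference in placebo response between the Parts therefore passes into the 700 mg estimate.

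The pooled 1050 mg test is in a different position. It has active and placebo participants in both Parts, so a within-Part contrast exists in each. For 700 mg, the Part 1 stratum holds no active participants. Adding Part as a stratification factor would remove the Part 1 placebo data from the comparison and would not rescue n=75.

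No planned analysis addresses this. Site and Hurley stage are the only randomisation factors. The robustness analyses named in 9.4.2.1.3 concern missing data and the per-protocol population, and the subgroups for the primary endpoint are not specified. At stake is whether a positive or negative 700 mg result would reflect the drug or the change in population.

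**Working it through.** **Inputs.** Part 1 placebo: 150/3 = 50 (6.3). Part 2 placebo: 25; Part 2 700 mg: 50 (6.3). Total placebo 50 + 25 = 75, which matches 9.2. The documents give the total; the split follows from the allocation. Placebo rates 25-35%, a 25-point effect, two-sided alpha 0.10 (9.2 and Table 3).

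**Step 1: reproduce the stated power (50 vs 75).** Power = Φ[(Δ − 1.645·SE0)/SE1], with SE0 pooled and SE1 unpooled. For 25% vs 50%, the pooled rate is (75×0.25 + 50×0.50)/125 = 0.35. Then SE0 = √[0.35×0.65×(1/75 + 1/50)] = 0.0871 and SE1 = √[0.25×0.75/75 + 0.5×0.5/50] = 0.0866. Power = Φ[(0.25 − 0.1432)/0.0866] = 89.1%. At placebo rates of 30% and 35% the results are 87.9% and 87.2%. Table 3 prints 89%, 87% and 87%. The stated power is correctly computed for n=75.

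**Step 2: concurrent control only (50 vs 25).** For 25% vs 50%, SE0 = 0.1208 and SE1 = 0.1118, so power = Φ[(0.25 − 0.1987)/0.1118] = 67.7%. At 30% and 35% it is 66.4% and 66.0%. Exact enumeration of the pooled Z-test gives 68.7%, 66.2% and 65.6%. Using the unpooled variance throughout gives 72.3%, 69.8% and 68.3%. About 66-69% is a fair summary, roughly 20 points below the stated figure.

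**Step 3: bias.** Let d = Part 1 placebo rate minus Part 2 placebo rate. The pooled control has expectation p + (50/75)d, where p is the Part 2 rate. The estimated 700 mg effect is therefore off by −(2/3)d. A 10-point d moves it by 6.7 points.

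**Step 4: error and power under assumed d.** Exact enumeration, placebo as Bin(50, p+d) + Bin(25, p), 700 mg as Bin(50, ·), reject if |Z| > 1.645. Each cell gives values for p = 25/30/35%. The error columns set the 700 mg rate equal to p.

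| d | False benefit | False harm | Power, 25-point effect |
|---|---|---|---|
| 0 | 5.2/5.1/5.2% | 5.0/5.0/5.0% | 89.3/88.2/87.3% |
| −10 points | 23.1/21.2/19.8% | 0.6/0.7/0.8% | 98.4/97.8/97.4% |
| +10 points | 0.7/0.8/0.9% | 19.8/19.0/18.3% | 66.8/65.4/64.8% |

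The d = 0 row agrees with step 1, so the model is the plan's own. For a smaller shift, d = −2.5 points gives 7.5-7.9% false benefit. The values of d are assumptions; the documents give no estimate. The figures are for the single test, ignoring its place in the sequence.

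**The case against.** The pooling is openly stated in 9.2, Estimand 2 and 9.4.2.1.3. A reader might infer that 87-89% is a miscalculation; it is not, because it reproduces under its assumptions. Borrowing placebo data across two parts of one protocol, with the same endpoint and the same Hurley and AN-count criteria, is an arguable trade-off for an optional Phase 2 arm tested at 0.10. That stands, and it is why the pooled test need not be removed.

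A reader might also infer that the design favours a false 700 mg success. The documents do not support a direction. The placebo HiSCR50 rates they quote (10%, 26%, 28% and 44%) come from separate trials, and the 10% is one of ten patients in an intravenous study. They do not measure a shift between Parts. That 10% came from patients with prior anti-TNF failure or unwilling to take adalimumab; if it pointed anywhere, it would suggest a lower Part 2 rate, where false claims of benefit fall below 1%. The only comparison by anti-TNF history (Protocol 2.2) shows 63% vs 61% response, although it is open-label and on active drug. Only some Part 2 participants would be adalimumab-experienced. If half were (an assumption), a 10-point d from this cause needs a 20-point placebo gap between experienced and naive participants.

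The test is also third in sequence. If no dose works, the familywise rate cannot exceed the rejection rate of comparison 1. The gate gives little protection when 1050 mg works, because comparisons 1 and 2 then usually pass.

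Finally, SAP sections 1 and 5.8 record termination for futility after the first interim analysis. SAP section 2 and 5.3.2.1 confine the hypothesis and estimand to 1050 mg versus placebo at Week 16 in Part 1. This stands in full and sets the priority.

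**Conclusion.** The point holds as a conditional statement about the protocol's design. Fifty of 75 placebo participants in comparison 3 were not randomised against 700 mg and were selected under different adalimumab rules, and the planned CMH test cannot correct for that. The 87-89% power and the 10% error rate rest on an unstated assumption of equal placebo rates across Parts. Departures bias the estimate by two thirds of d in size, with the consequences tabulated above for an assumed 10 points either way. The randomised control alone gives about 66-69% power.

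The documents do not establish that d differs from zero, or its sign. They also do not support reading this as a flaw in any reported result: no 700 mg analysis is in the SAP, and no Part 1 result changes. Priority is low.

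**What to change.** In Protocol 9.4.2.1.3, pre-specify 700 mg versus concurrently randomised Part 2 placebo at Week 12 (50 vs 25) as a required analysis reported beside the pooled test. Show the placebo HiSCR50 rates for Part 1 and Part 2 separately. Limit any 700 mg claim to results where the two analyses agree in direction and rough size.

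In Protocol 9.2 and Table 3, and where SAP section 3 repeats them, state that 87-89% assumes equal placebo rates across Parts and that concurrent-control power for a 25-point difference is about 66-69%.

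The cost is wording and one table, with no change to enrolment or allocation. Making the concurrent comparison the formal third test is an option, at a cost of about 20 points of power. Because the study has stopped, the practical use is to label the power statement correctly and to carry the rule into any later design that adds an arm after a control group has been enrolled.

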#### **9.4.2.2. Secondary Endpoints**

In addition to the primary endpoint analysis, the analyses for secondary efficacy endpoints will be performed. No adjustments for multiple comparisons will be made for the secondary endpoints and nominal p-values will be provided. The efficacy endpoints will also be summarized over time. Additional efficacy analyses may be performed and will be documented in the SAP.

- The proportion of participants who achieved HiSCR75 and HiSCR90 at Week 16 in Part 1, and at Week 12 in Part 2 will be compared between each of the bermekimab groups and the placebo group.
- The change from baseline in AN count at Week 16 in Part 1, and at Week 12 in Part 2 will be compared between each of the bermekimab groups and the placebo group.
- The proportion of participants achieving at least 50%, 75%, 90%, and 100% reduction in total AN count at Week 16 in Part 1, and at Week 12 in Part 2 will be compared between each of the bermekimab groups and the placebo group.
- The proportion of participants achieving AN count of 0/1 and 0/1/2 at Week 16 in Part 1, and at Week 12 in Part 2 will be compared between each of the bermekimab groups and the placebo group.
- The proportion of participants who achieved complete elimination of abscesses at Week 16 in Part 1, and at Week 12 in Part 2 will be compared between each of the bermekimab groups and the placebo group among participants who had any abscess at baseline.
- The change from baseline in number of abscesses at Week 16 in Part 1, and at Week 12 in Part 2 will be compared between each of the bermekimab groups and the placebo group.
- The proportion of participants who achieved complete elimination of draining fistulas at Week 16 in Part 1, and at Week 12 in Part 2 will be compared between each of the bermekimab groups and the placebo group among those with draining fistulas at baseline.
- The change from baseline in number of draining fistulas at Week 16 in Part 1, and at Week 12 in Part 2 will be compared between each of the bermekimab groups and the placebo group.
- The proportion of participants who achieved complete elimination of inflammatory nodules at Week 16 in Part 1, and at Week 12 in Part 2 will be compared between each of the bermekimab groups and the placebo group among those with inflammatory nodules at baseline.

- The change from baseline in international hidradenitis suppurativa severity score (IHS4) at Week 16 in Part 1, and at Week 12 in Part 2 will be compared between each of the bermekimab groups and the placebo group.
- The change from baseline in number of inflammatory nodules at Week 16 in Part 1, and at Week 12 in Part 2 will be compared between each of the bermekimab groups and the placebo group.
- The proportion of participants with HS-IGA score of inactive (0), almost inactive (1), or mild (2) and with at least 2-grade improvement relative to baseline at Week 16 in Part 1, and at Week 12 in Part 2 will be compared between each of the bermekimab groups and the placebo group.
- The proportion of participants with HS-IGA score of inactive (0), almost inactive (1) at Week 16 in Part 1, and at Week 12 in Part 2 among participants with HS-IGA score of moderate (3) or severe (4) at baseline will be compared between each of the bermekimab groups and the placebo group.
- The change from baseline in DLQI at Week 16 in Part 1, and at Week 12 in Part 2 will be compared between each of the bermekimab groups and the placebo group.
- The change from baseline in HSSD-24h total symptom score at Week 16 in Part 1, and at Week 12 in Part 2 will be compared between each of the bermekimab groups and the placebo group.
- The change from baseline in pain scale score of HSSD-24h at Week 16 in Part 1, and at Week 12 in Part 2 will be compared between each of the bermekimab groups and the placebo group.
- The change from baseline in itch scale score of HSSD-24h at Week 16 in Part 1, and at Week 12 in Part 2 will be compared between each of the bermekimab groups and the placebo group.

The comparison between the adalimumab and placebo groups for the secondary endpoints at Week 16 in Part 1 listed above will also be performed at a 2-sided significance level of 0.1. Nominal p-values will be reported. No adjustments for multiple comparisons will be made for the secondary endpoints.

In addition, to assess the relative efficacy between the bermekimab and adalimumab groups, for selected binary endpoints (including HiSCR50 at Week 16), the difference in proportion of participants achieving these endpoints at Week 16 and Week 32 in Part 1 between the bermekimab group and the adalimumab group, and the corresponding 80% CIs, will be calculated. No hypothesis testing will be performed.

